### **1.7 Secondary Objectives**

- To evaluate the difference in pain from local anesthetic infiltration with J-tip needless injection compared to needle injection.
- To evaluate efficacy of femoral and/or sciatic nerve block after J-tip lidocaine injection compared to needle injected lidocaine post operatively by tracking pain levels to post operative day three.
- To assess patient and parent satisfaction with J-tip use.
- To assess changes in post operative pain medication amounts with J-tip use.
- To evaluate changes in post operative nausea and/or vomiting with J-tip use.
- To evaluate changes in post operative anti-nausea/anti-emetic medication use with J-tip use.
- To evaluate changes in time of PACU stay.

- To assess any differences in outcomes or pain after J-tip or needle injected lidocaine with respect to BMI, thigh circumference, gender, ethnicity or operative time in pain reporting measures, satisfaction or medication usage.

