No statistical significance when comparing means Injection Type the following variables: 1st Type of Sedation, 1st Total Quantity of sedation used (mg), 2nd Type of Sedation Used, Total Quantity 2nd Type of sedation used (mcg), 3rd Type of Sedation Used, Total Quantity 3rd Type of sedation used (mcg), Visual Analog Scale (VAS) prior to local femoral, VAS prior to femoral, VAS immediately after femoral, VAS prior to local sciatic, VAS prior to sciatic, VAS immediately after sciatic, VAS prior to PACU Discharge.

VAS Immediately After Local Femoral:

Ordinary Least Squares Regression is utilized to determine if the Visual Analog Scale (VAS) immediately after local femoral for Needle Injections is significantly different from J-Tip Injections. This regression is run to determine if the injection type can statistically predict VAS immediately after local femoral. There is an independence of residuals, as assessed by a Durbin-Watson statistic, of 1.688 (Table 4). The assumptions of linearity, independence of errors, homoscedasticity, unusual points, and normality of residuals were met. The model is statistically significant,  $F (6, 100) = 10.215, p \leq .001$ , adj.  $R^2 = .343$ . Injection type statistically significantly predicts VAS immediately after local femoral, as seen in Table 3,  $\beta = -2.020, t = -6.266, p \leq .001$ . The beta explains that if a J-tip injection was given it would decrease the VAS immediately after local femoral by approximately 2. Regression coefficients and standard errors can be found in Appendix.

Variable	Adjusted R 	Model			Injection Type		
		df	F	Sig.	Beta	T	Sig.
VAS Immediately After Local Femoral	.343	6	10.215	.000	-2.020	-6.266	.000

Table 3: Beta Explanation for VAS Immediately After Local Femoral

Model	R	R 	Adjusted R 	Standard Error of the Estimate	Durbin-Watson
1	.616 a	.380	.343	1.656	1.688

- Predictors: (Constant), Thigh Circumference (cm), Ethnicity, Injection Type, Age, Gender BMI
- Dependent Variable: VAS Immediately After Local Femoral

Table 4: Model Summary

Model		Sum of Squares	df	Mean Square	F	Sig.
1	Regression	168.140	6	28.023	10.215	.000 b
	Residual	274.327	100	2.743		
	Total	442.467	106			

a. Dependent Variable: VAS Immediately After Local Femoral  
b. Predictors: (Constant), Thigh Circumference (cm), Ethnicity, Injection Type, Age, Gender BMI

Table 5: ANOVAa

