		Unstandardized Coefficients		Standardized Coefficients				95% Confidence Interval for B	
Model		B	Std. Error	Beta	t	Sig.	Lower Bound	Upper Bound	
1	(Constant)	9.774	2.119		4.613	.000	5.570	13.977	
	Injection Type	-2.020	.322	-.496	-6.266	.000	-2.660	-1.381	
	Gender	.504	.340	.124	1.481	.142	-.171	1.179	
	Age	-.250	.105	-.193	-2.367	.020	-.459	-.040	
	Ethnicity	-.021	.117	-.014	-.177	.860	-.253	.212	
	BMI	-.079	.065	-.186	-1.225	.223	-.208	.049	
	Thigh Circumference (cm)	-.021	.038	-.083	-.545	.587	-.097	.055	

a. Dependent Variable: VAS Immediately After Local Femoral

Table 7: Coefficientsa

VAS immediately after local sciatic:

Ordinary Least Squares Regression is utilized to determine if the Visual Analog Scale (VAS) immediately after local sciatic for Needle Injections is significantly different from J-Tip Injections. This regression is run to determine if the injection type can statistically predict VAS immediately after local sciatic. There is an independence of residuals, as assessed by a Durbin-Watson statistic, of 1.798 (Table 9). The assumptions of linearity, independence of errors, homoscedasticity, unusual points, and normality of residuals were met. The model is statistically significant,  $F(6, 100) = 6.178$ ,  $p \leq .001$ , adj.  $R^2 = .227$ . Injection type statistically significantly predicts VAS immediately after local sciatic, as seen in Table 8  $\beta = -2.248$ ,  $t = -5.191$ ,  $p \leq .001$ . The beta explains that if a J-tip injection was given it would decrease the VAS immediately after local sciatic by approximately 2. Regression coefficients and standard errors can be found in Appendix.

Variable	Adjusted R 	Model			Injection Type		
		df	F	Sig.	Beta	T	Sig.
VAS Immediately After Local Sciatic	.277	6	6.178	.000	-2.248	-5.191	.000

Table 8: Beta Explanation for VAS Immediately After Local Sciatic

Model	R	R 	Adjusted R 	Standard Error of the Estimate	Durbin-Watson
1	.520 a	.270	.227	2.2247	1.798

c. Predictors: (Constant), Thigh Circumference (cm), Ethnicity, Injection Type, Age, Gender BMI

d. Dependent Variable: VAS Immediately After Local Sciatic

Table 9: Model Summary

Model		Sum of Squares	dF	Mean Square	F	Sig.
1	Regression	183.449	6	30.575	6.178	.000 b
	Residual	494.930	100	4.949		
	Total	678.379	106			

c. Dependent Variable: VAS Immediately After Local Sciatic

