d. Predictors: (Constant), Thigh Circumference (cm), Ethnicity, Injection Type, Age, Gender BMI

Table 10: ANOVAa

		Unstandardized Coefficients		Standardized Coefficients				95% Confidence Interval for B	
Model		B	Std. Error	Beta	t	Sig.	Lower Bound	Upper Bound	
1	(Constant)	9.130	2.846		3.208	.002	3.484	14.777	
	Injection Type	-2.248	.433	-.446	-5.191	.000	-3.107	-1.389	
	Gender	.826	.457	.164	1.807	.074	-.081	1.179	
	Age	-.236	.142	-.147	-1.665	.099	-.517	-.040	
	Ethnicity	.005	.157	.003	.033	.973	-.307	.212	
	BMI	-.029	.087	-0.54	-.329	.743	-.201	.049	
	Thigh Circumference (cm)	-.028	.051	-.090	-.543	.588	-.130	.055	

b. Dependent Variable: VAS Immediately After Local Sciatic

Table 11: Coefficientsa

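### Both regressions give ethnicity one slope on codes spanning at least three units, most likely a nominal factor fitted as a linear score, and Table 11 misprints its upper confidence limits

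*Combined protocol and SAP*

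**What the plan says.** Section 1.7 (Secondary Objectives) sets out "To assess any differences in outcomes or pain after J-tip or needle injected lidocaine with respect to BMI, thigh circumference"; the list goes on to gender, ethnicity and operative time, and covers pain reporting, satisfaction and medication use. Section 4 names ethnicity among the demographics to be considered. Section 7 allows for regression where adjustment seems necessary and gives no rule for coding categorical covariates.

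The Results report two OLS models, for VAS immediately after the local femoral and the local sciatic injection. Each lists the same terms: "Predictors: (Constant), Thigh Circumference (cm), Ethnicity, Injection Type, Age, Gender BMI". The femoral ANOVA (Table 5) has a regression line of "168.140 6 28.023 10.215" and a residual line of "274.327 100 2.743". The sciatic model (Table 10) also has 6 and 100 degrees of freedom.

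Each coefficient table has one ethnicity row:

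- Table 7, femoral: "Ethnicity -.021 .117 -.014 -.177 .860 -.253 .212"
- Table 11, sciatic: "Ethnicity .005 .157 .003 .033 .973 -.307 .212"

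The available text shows no category list, reference category, counts or treatment-by-ethnicity term. The text under each model interprets injection type only.

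**The concern.** Ethnicity is nominal. If several categories are numbered and entered as one term, the model assumes that they are ordered and equally spaced. The sign, size and p-value of the slope then depend on who was given which number. The Results say that linearity was met, which has no meaning for arbitrary category numbers.

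At stake is the ethnicity part of a listed secondary objective. These two rows are the only ethnicity results in the documents. A reader who sees p-values of .860 and .973 could take them as evidence of no ethnic difference, and a flat slope across arbitrary codes cannot show that.

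**Working it through.** **Inputs.** Femoral (Tables 4, 5, 7): sums of squares 168.140 (6 df), 274.327 (100 df) and 442.467 (106 df), so n = 107; residual SD s = 1.656; ethnicity B = -.021, SE = .117, standardized Beta = -.014. Sciatic (Tables 9 to 11): sums of squares 183.449, 494.930 and 678.379 on the same df; s = 2.2247; ethnicity B = .005, SE = .157.

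**1. Reproduce the printed models.**
- Femoral: F = (168.140/6)/(274.327/100) = 10.215; R² = 168.140/442.467 = .380; adjusted R² = 1 - (1 - .380) × 106/100 = .343. All agree with print.
- Sciatic: F = 6.178, R² = .270, adjusted R² = .227. These agree with the text and Table 9; Table 8 prints .277.

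**2. Degrees of freedom.** Six named predictors on 6 df leave exactly 1 df for ethnicity. With k categories as indicators, model df would be 5 + (k - 1): 7, 8, 9 or 10 for k = 3, 4, 5 or 6.

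**3. SD of the ethnicity variable.** In OLS, SE² = s²/[(n - 1) × SD² × (1 - R²x)], where R²x comes from regressing ethnicity on the other predictors. Hence SD ≥ s/(SE × √106), and any correlation with the other predictors only raises it.
- Femoral: 1.656/(.117 × 10.296) = 1.375 (1.369 to 1.381 over rounding of the SE).
- Sciatic: 2.2247/(.157 × 10.296) = 1.376 (1.372 to 1.381).
- Second route, femoral: SD = |Beta| × SD of VAS/|B|, with SD of VAS = √(442.467/106) = 2.043. This gives .014 × 2.043/.021 = 1.36 (1.28 to 1.45 over rounding).

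**4. Compare with a 0/1 variable.** Its largest SD at n = 107 is 0.5 × √(107/106) = 0.502. The second route returns that value for known two-level variables. Gender ("Gender .504 .340 .124 1.481 .142") gives .124 × 2.043/.504 = 0.50, and injection type gives .496 × 2.043/2.020 = 0.50.

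**5. Span of the codes.** An SD of 1.369 needs a range of at least 2 × 1.369 × √(106/107) = 2.73, so integer codes span at least 3.

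**6. What renumbering can do (assumed data, not the trial's).** Take five groups of 40, 20, 30, 10 and 7 with assumed means 2.0, 3.2, 2.6, 3.5 and 2.2, within-group SD 1.656 and codes 1 to 5. Over all numberings the code SD runs from 1.04 to 1.71, which brackets 1.37. In one simulated set the slope runs from -0.334 to 0.334 and its p-value from 0.0027 to 0.994; the joint test, which ignores numbering, gives p = 0.060. In a second set the p-value runs from 0.0003 to 0.987, with joint p = 0.010. This shows the mechanism only.

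**7. Upper limits in Table 11.** With t(.975, 100) = 1.984, each upper limit should be B + 1.984 × SE.

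| Covariate | Table 7 prints | Table 11 prints | Table 11 recomputed |
|---|---|---|---|
| Gender | 1.179 | 1.179 | 1.733 |
| Age | -.040 | -.040 | .046 |
| Ethnicity | .212 | .212 | .316 |
| BMI | .049 | .049 | .144 |
| Thigh circumference | .055 | .055 | .073 |

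All five printed limits repeat Table 7. The sciatic ethnicity interval as fitted is about -.306 to .316. The age row shows the error on its face: its interval excludes zero while its p-value is .099.

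**The case against.** The strongest objection is that the coding is inferred. One might infer from the SD that at least four categories were scored, but the calculation bounds the span of the codes and not the number of levels. Codes 1, 2 and 4 would fit. So would just two groups coded 1 and 4: 9p(1 - p) = 1.375² × 106/107 = 1.873 gives p = .295, a split of about 30/70. Codes 1 and 5 fit at about 13/87. With two groups the p-value is a valid contrast that renumbering cannot change. The Results also point to an appendix that is not in the available text. This objection stands: the multi-category reading is the likelier one, but it is not proven.

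Second, the trial does not claim that ethnicity has no effect. The stated purpose of each regression is to test injection type, and ethnicity serves as an adjustment covariate. That also stands. The problem lies in the printed rows and in what they could be used for.

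Third, recoding alone would not meet the objective. Section 1.7 concerns differences after one or the other injection method, across pain, satisfaction and medication use, whereas both models have main effects only and cover two VAS outcomes. This is correct and widens the fix.

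Fourth, little depends on these rows for the main comparison. This is accepted. None of these objections touches the upper-limit error in Table 11, which needs no assumption about coding.

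**Conclusion.** The point holds in a limited form. It is certain that ethnicity has one slope in each model. Given the printed standard errors and integer codes, it is not a 0/1 indicator and its codes span at least three units. Most likely several nominal categories were scored as equally spaced. If so, the ethnicity slopes, intervals and p-values (.860 and .973) depend on the numbering and cannot inform the ethnicity objective.

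A reader might go further in two ways that the documents do not support. One is that a real ethnic difference has been hidden. Nothing shows this, because the corrected test needs category counts and patient data that are not given. The other is that the treatment result is compromised. The femoral difference is 2.030 unadjusted and 2.020 adjusted, and the sciatic 2.228 and 2.248. The unadjusted figures use 111 patients and the adjusted ones 107, so the comparison is not exact, but in a randomized comparison recoding one covariate should move the estimate little.

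The five Table 11 upper limits are wrong however ethnicity was coded.

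**What to change.** 1. State the ethnicity categories, their numeric codes and the counts by arm.
2. If there are more than two categories, refit both models with indicator variables and a named reference, combining sparse categories. Report one joint F test for ethnicity, replace the ethnicity rows in Tables 7 and 11, and update model df, F and adjusted R². If there are only two, say so and label the contrast.
3. Add a treatment-by-ethnicity test to each model, labelled exploratory, because the objective concerns differences after J-tip or needle injection. Say that satisfaction and medication use by ethnicity are not covered by these two models.
4. Correct the five covariate upper limits in Table 11. If the model is left as fitted, the ethnicity interval is about -.306 to .316.

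The cost is two re-run regressions. For three to six categories, indicators take 1 to 4 more of the 100 residual degrees of freedom (leaving 99 to 96), and the interaction takes a further k - 1 in its own model. No new data are needed.

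### BMI and thigh circumference are collinear in the femoral regression, so their separate p-values (.223 and .587) should not be read as absence of a body-size association

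*Combined protocol and SAP*

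**What the plan says.** Section 1.7 (Secondary Objectives) includes: "To assess any differences in outcomes or pain after J-tip or needle injected lidocaine with respect to BMI, thigh circumference", followed by further factors. Section 3.2 does not repeat this objective. Section 4 lists BMI and thigh circumference among the measurements to be considered and defines where the thigh is measured.

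The Results section reports one regression per infiltration site. For the femoral site the predictor list under Tables 4 and 5 is "Predictors: (Constant), Thigh Circumference (cm), Ethnicity, Injection Type, Age, Gender BMI", and the coefficient table (Table 7) carries the footnote "Dependent Variable: VAS Immediately After Local Femoral". Its two body-size rows, in the order B, standard error, standardized beta, t, p and 95% limits, are:

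- "Thigh Circumference (cm) -.021 .038 -.083 -.545 .587 -.097 .055"
- "BMI -.079 .065 -.186 -1.225 .223 -.208 .049"

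The text lists assumptions as met; collinearity is not among them. No VIF, no joint test and no model with a single body-size measure is printed. The narrative interprets injection type only.

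**The concern.** BMI and thigh circumference are two measures of body size. When each is tested with the other held fixed, most of their shared information is credited to neither, and both can look null even if body size matters. Here both coefficients are negative, and the standard error of each is almost doubled (square root of 3.72 = 1.93).

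At stake is the body-size part of the section 1.7 objective. Table 7 is the only evidence in the results on body size and femoral infiltration pain. A reader who consults it sees two unremarkable p-values and may conclude that neither measure is related to pain. The tables themselves point the other way.

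**Working it through.** **Inputs (femoral model).** From Table 5: regression sum of squares 168.140 on 6 df, "Residual 274.327 100 2.743" and "Total 442.467 106". From Table 7: standardized betas and t values. No significance level is stated; two-sided 5% is assumed from the 95% intervals in section 7.

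**Reproducing the printed figures.** F = (168.140/6)/(274.327/100) = 10.215. R² = 168.140/442.467 = .380. Adjusted R² = 1 − (274.327/100)/(442.467/106) = .343. On 100 df, t = −1.225 gives p = .223 and t = −.545 gives p = .587. All agree with the tables.

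**Implied VIFs.** VIF = (standardized beta / t)² × 100 / (1 − R²).

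| Predictor | beta | t | VIF |
|---|---|---|---|
| BMI | −.186 | −1.225 | 3.72 |
| Thigh circumference | −.083 | −.545 | 3.74 |
| Gender | .124 | 1.481 | 1.13 |
| Age | −.193 | −2.367 | 1.07 |
| Injection type | −.496 | −6.266 | 1.01 |
| Ethnicity | −.014 | −.177 | 1.01 |

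Rounding of the printed values moves the first two only to 3.70–3.74 and 3.69–3.79. The other four are near 1, so the inflation comes from BMI and thigh circumference with each other.

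**Size of the partial correlation r.** If the other four predictors explained none of BMI, r = √(1 − 1/3.72) = .855. Allowing them the overlap that their own VIFs permit lowers r. A numerical search over predictor correlation matrices matching all six VIFs puts |r| at about .82 to .855.

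**Sign of r.** R² equals the sum of each standardized beta times that predictor's correlation with the outcome. Treating the other predictors as uncorrelated, the squared betas sum to .340, and the BMI–thigh term is 2 × (−.186) × (−.083) × r = ±.026 at r = ±.855. That gives R² of about .367 for positive r and .314 for negative r; the printed value is .380. In the full search, negative r reached at most about .363. So r is positive.

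**Joint test.** The two estimates have correlation −r, so F = (t₁² + t₂² + 2r·t₁t₂) / [2(1 − r²)] on 2 and 100 df. Here t₁² + t₂² = 1.501 + .297 = 1.798 and t₁t₂ = .668.

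**One measure alone.** t² = (2F − t²_other) × 101/(100 + t²_other).

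| r | Joint F | p | BMI alone, abs. t | Thigh alone, abs. t |
|---|---|---|---|---|
| .82 | 2.893/.655 = 4.41 | .015 | 2.93 | 2.70 |
| .84 | 4.96 | .009 | 3.11 | 2.89 |
| .855 | 2.939/.538 = 5.46 | .006 | 3.27 | 3.06 |

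Both single-measure associations are negative. The joint p falls below .05 once r exceeds about .74, which is under the supported range. The pair's share of R² is 2F(1 − R²)/100, about .055 to .068. Age, the only covariate apart from injection type printed as significant, contributes 2.367² × .620/100 = .035.

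**Sciatic model.** Using t = −.329 and −.543 over the same r, joint F is about 1.06 to 1.32, p about .35 to .27. This remains null.

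**The case against.** Several parts of the opposing case stand.

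- **No false statement is made.** A reader might infer that the trial reports no relation between body size and pain, and that a joint test would overturn that answer. The documents do not support this. The regression's stated purpose is to see whether injection type predicts pain, and no sentence concludes anything about body size. The objective is unanswered rather than wrongly answered.
- **Joint entry is not an error.** Adjusting the treatment comparison for both measures is legitimate, and the injection-type VIF is 1.01. The two p-values are correct for the narrow question that each asks. They should be supplemented, not removed.
- **The signal is post hoc and femoral only.** It is reconstructed from rounded tables. Section 1.7 spans five factors and several outcomes. Counting only five factors by two VAS outcomes (an assumption), a Bonferroni threshold would be .05/10 = .005, and the joint p of .015 to .006 misses it.
- **The test basis is imperfect.** The calculation uses ordinary least-squares standard errors, although Levene's test for the femoral VAS gives p = .036 in Table 2. Section 7 plans exact and non-parametric tests, with regression where adjustment is needed.
- **The objective is ambiguous.** It can be read as asking whether the J-Tip versus needle difference varies with body size. A main-effect test does not address that.

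None of this makes the mutually adjusted p-values a suitable answer to the objective on its main-effect reading.

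**Conclusion.** The point holds as a limit on interpretation. The femoral tables imply substantial collinearity between BMI and thigh circumference. They also imply a negative joint association with infiltration pain that neither separate p-value shows: F about 4.4 to 5.5, p about .015 to .006.

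The VIFs follow directly from printed figures. The joint result also rests on r, which is not printed. Its range of about .82 to .855 and its positive sign are inferred from the VIFs and R², and must be confirmed on the data. The result is exploratory, unadjusted for multiplicity, and a main effect only.

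It does not establish that body size affects pain, says nothing about effect modification, does not extend to the sciatic site, and does not touch the treatment comparison.

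**What to change.** Leave the treatment model and its coefficients as they are. For the BMI and thigh-circumference objective, add for both the femoral and sciatic outcomes either a joint 2-df test of the two measures or one model per measure with the other left out. Compute these from the data, and label them exploratory and without multiplicity adjustment. State beside Table 7 that the two separate p-values are each conditional on the other measure. If the objective is meant as effect modification, say so and add a treatment-by-body-size interaction.

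The cost is one F test or two extra regressions per outcome on data already held, plus the interaction model if it is wanted.
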